15.3 Causality: Serious Adverse Event and Adverse Event Relationship to Study Treatment

The Investigator will assess the relationship of the SAE and AE to study device placement procedure (procedure) or study device by using the following general guidelines:

Not Related: A causal relationship between the study device and the AE can be ruled out (e.g., based on the temporal sequence, absence of a reasonable pathophysiological mechanism, or direct evidence of actual cause).

Unlikely related: A clinical event, including laboratory test abnormality, with a temporal relationship to procedure or study device initiation which makes a causal relationship improbable, and in which other drugs, chemicals or underlying disease provide plausible explanations.

Probably Related: A clinical event, including laboratory test abnormality, with a reasonable time sequence to first attempt of study device placement, unlikely to be explained by concurrent disease or other drugs or chemicals. Information on drug withdrawal may be lacking or unclear.

Related: A clinical event, including laboratory test abnormality, with a reasonable time sequence to first attempt of study device placement, cannot be attributed to concurrent disease or other medical devices, drugs, or chemicals, and which follows a clinically reasonable response on withdrawal.

15.3.1 Clarification of Adverse Events Related to Study Procedures

Any untoward event that occurs from the beginning of the study device placement procedure until completion of placement, or from the beginning of the removal procedure until the completion of removal, will be reported as an AE. The AE should be recorded on the AE eCRF with a causality assessment of "related to study device placement procedure." If the AE also meets the criteria for an SAE, an SAE eCRF should be completed and submitted to Sponsor.

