Effectiveness will be evaluated as the absence of pregnancy during VeraCept use for up to12 months. Pregnancies judged to have occurred during study device use (determined by ultrasound and medical assessments), for which the estimated date of conception was within 7 days after study device removal or calculated date of expulsion, will be included in the per protocol analysis of pregnancies.

The Pearl Index (and 95% confidence intervals) will be calculated through 12 months for cycles in subjects aged 18-35 at the time of study device placement, excluding the following cycles (unless the subject became pregnant in the cycle):

- When back-up contraceptive or emergency contraceptive use was documented on the daily diary
- When the subject denied having any intercourse.

All pregnancies will be counted in the intent to treat analysis.

Life table analyses will be used as further assessment of pregnancies. Secondarily the Pearl index and life table analyses will be done through 3 years.

Safety and Other Outcome Measures

VeraCept ease of placement, removal and placement success will be descriptively summarized.

Safety evaluations will be based on the incidence of adverse events and serious adverse events changes from baseline in other assessments (examinations and vital signs) and by relationship to the study device or study device placement procedure. Study device tolerability will be based on changes in bleeding and spotting patterns and study discontinuation (including reasons for discontinuation).

Safety analyses will be based on the experience of all subjects who had attempted study device placement and provided any relevant data. Tolerability analyses will be based on the experience of all subjects who received a study device and provided any relevant data.

Subjects will record frequency and intensity of vaginal bleeding through a daily diary. The number of bleeding or spotting days will be summarized for each cycle. In addition, bleeding and spotting will each be summarized separately. Bleeding analyses will include all subjects who had a study device placed and have at least 1 cycle where they were not pregnant and were providing bleeding-related diary data on the days in the reference period.

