20.7 Safety And Other Outcome Measures

All safety and other outcome measures will be analyzed using the ITT/Safety Population unless noted otherwise. Confidence intervals will be provided to support interpretation of the observed safety rates.

VeraCept Characteristics

Study device ease of placement and placement success will be summarized. Cumulative study device expulsion rates will be summarized

Adverse Events

The number and percentage of subjects with each adverse event and serious adverse event will be presented in a table by MedDRA system-organ class and preferred term. Summaries will also be presented by relationship to the VeraCept placement or removal procedure and the severity of the adverse event. All adverse events will be summarized with special attention to those events that may be related to an intrauterine contraceptive, including:

- Anemia
- Back pain
- Dysmenorrhea
- Dyspareunia
- Ectopic pregnancy
- Embedment, which in some cases may require surgical removal

- Expulsion, partial or complete
- Intrauterine pregnancy
- Leukorrhea
- Medical diathermy
- Menstrual flow, prolonged / vaginal bleeding
- Menstrual spotting
- Movement of study device during MRI
- Pain and cramping
- Pelvic infection, which can lead to Fallopian tubal damage leading to ectopic pregnancy or infertility, hysterectomy, sepsis and rarely death
- Pelvic Inflammatory Disease (PID), which can lead to tubal damage leading to ectopic pregnancy or infertility, or infrequently can necessitate hysterectomy, or cause death.
- Uterine perforation, which may lead to pre-operative imaging followed by laparscopy or laparotomy to remove the IUD from the peritoneal cavity
- Septic abortion
- Uticarial allergic skin reaction
- Vaginitis
- Vasovagal reaction at the time of placement, including fainting.

VeraCept Safety-Related Removal Rates and Expulsion Rates

Cumulative VeraCept safety-related removal rates and expulsion rates at each year will be summarized.

Bleeding and Spotting Patterns

Vaginal bleeding and spotting will be recorded daily by the subject in her diary. The ECYC population will be used for the bleeding and spotting summaries. The number of bleeding or spotting days will be summarized for each cycle. In addition, bleeding and spotting will be summarized separately. Subjects who discontinue the study due to bleeding complaints prior to completing one 28-day cycle will be included in the bleeding analysis.

Other Safety Assessments

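### Protocol 15.3.1 gives events during device removal a placement-procedure causality label, so the causality field as specified cannot separate the two procedures named in 20.7

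*Protocol*

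**What the plan says.** Protocol 15.3.1 sets two windows in which any untoward event counts as an adverse event. One runs from the start to the completion of placement. The other is added in the same sentence: "or from the beginning of the removal procedure until the completion of removal, will be reported as an AE". The following sentence tells the site how to code such an event: "The AE should be recorded on the AE eCRF with a causality assessment of" being related to the placement procedure. No other value is given for the removal window.

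Protocol 15.3 defines what causality is judged against: "The Investigator will assess the relationship of the SAE and AE to study device placement procedure (procedure) or study device". Its two upper categories, Probably Related and Related, both require an event "with a reasonable time sequence to first attempt of study device placement".

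Protocol 20.7 sets out the reporting: "Summaries will also be presented by relationship to the VeraCept placement or removal procedure", and by severity. The synopsis (Statistical Methods, Safety and Other Outcome Measures) instead has safety evaluated "by relationship to the study device or study device placement procedure", with no mention of removal.

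SAP 3.8.2 plans adverse event tables by relatedness to the study product on a four-level scale from Not Related to Related. Neither that section nor the table list in SAP 5.2 contains a table by relationship to the placement or the removal procedure.

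**The concern.** The coding rule is explicit, and it points the wrong way for one of its two windows. Devices are removed at Week 52, at 3 years, or earlier on request. A site that follows 15.3.1 for an event during any of these removals records it as caused by insertion.

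Two things follow for anyone using the field. A count of placement-related events would include events that did not arise from placement. Removal-related events would have no value of their own. The study is meant to support a Phase III programme, and its objectives include both device placement and safety. Section 20.7 also singles out events bearing on retrieval, such as embedment that may need surgical removal. Section 6.2 lists procedural pain and post-procedural haemorrhage among events seen in more than 2% of subjects in the first year. Those terms do not say which procedure was involved, and the causality field is where one would look to find out.

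**Working it through.** No design figure is involved, so the check sets the passages side by side.

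1. **Which events does the rule cover?** Protocol 15.3.1 covers placement-window and removal-window events, joined in one sentence.
2. **What label do they get?** One label, naming placement. The coding sentence refers back to the adverse event just defined and makes no distinction between the windows.
3. **Does 15.3 supply a removal target?** No. The targets are the placement procedure and the device. The time anchor for the two upper categories is the first placement attempt, which an event at a 3-year removal cannot sensibly satisfy. Sections 15.3 and 15.3.1 therefore pull in different directions for such an event.
4. **What does the reporting section expect?** Section 20.7 names placement or removal. It does not say whether these form one pooled category or two. The synopsis names device or placement only, so the protocol is not consistent with itself.
5. **Does the SAP resolve it?** No. SAP 3.8.2 and 5.2 deal with relatedness to the study product. A procedure table built later from the causality value alone would inherit the label in step 2.
6. **Is there another route to the split?** In part. SAP 3.8.2 lists onset dates for serious events and for events leading to discontinuation. SAP 3.2 uses the device removal date, and Listings 16.2.5.2 (removal) and 16.2.7.1 (adverse events) are planned. Matching onset date to removal date gives an approximate split. A date match does not show that the event fell within the procedure or was caused by it. Protocol 12.5 provides for removal because of an adverse event, so an event with same-day onset may be the reason for removal.

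**Direction and size.** Let P be the number of events in the placement window and R the number in the removal window. Recorded as instructed, the placement label carries P + R, an excess of R/P relative to P, and no value identifies the R removal events. The direction is fixed by the rule. The documents give neither P nor R, so the ratio cannot be evaluated.

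**The case against.** The strongest reply is that little in the planned output depends on this label. The SAP reports relatedness to the product, so no listed table shows a placement-related count that could be inflated. Removal ease and subject-rated removal pain are summarised apart from placement (SAP 3.8.3, Table 14.3.6). Adverse event summaries by onset period put late removals in different periods from insertion-day events. The 15.3.1 windows are narrow, running only from the start to the completion of a procedure.

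Much of this is correct, and it limits the point. It does not remove it. Section 20.7 promises a procedure summary, and leaving it out of the SAP is a further gap. The schedule marks removal ease and pain at Week 52/Exit only, and the 3-year exit list in Protocol 12.4 includes removal without them, so they are a weak substitute in the extension. Onset-period tables mix removal events with every other event in the period.

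A reader might also infer more than the documents support:

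- **That the 20.7 summary cannot be produced.** A pooled placement-or-removal category would satisfy one reading of 20.7, and dates allow an approximate split.
- **That removal-related events will be reported as zero.** The AE eCRF (dated 30JAN2018 in SAP 1.0) is not available, and it may hold a removal field that the protocol does not describe.
- **That the placement count is overstated by a particular percentage.** Any such figure would rest on assumed numbers of removals and assumed event rates.
- **That safety of placement is itself a stated objective.** Protocol 5 lists placement and safety separately, and the placement outcomes in 5.2 are success and ease, which do not use the causality label.

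**Conclusion.** The point holds as an inconsistency in how attribution is collected. Protocol 15.3.1 assigns removal-window events to placement, 15.3 offers no alternative, and the resulting field cannot by itself distinguish the procedures that 20.7 names. The synopsis and the SAP do not agree with 20.7 either.

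The misattribution runs in one direction, and its size is unknown. The conclusion rests on the literal protocol text and on sites having followed it. If the eCRF already separates the procedures, the recorded data may be sound, but the protocol wording would still need to match. This should be corrected before the final safety tables are produced. It does not affect the Pearl Index or the placement success and ease outcomes.

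**What to change.** - **Protocol.** Reconcile the synopsis, 15.3, 15.3.1 and 20.7. In 15.3 and 15.3.1, keep the placement-procedure label for events in the placement window and give events in the removal window their own removal-procedure label.
- **eCRF.** Add a matching causality option to the AE form if none exists.
- **SAP.** Add to 3.8.2 and 5.2 one adverse event table by relationship to procedure, with placement and removal shown separately.
- **Existing records.** Reclassify only adverse events that already carry the procedure label and whose onset date equals the removal date, each confirmed by site query. Recoding every event with onset on the removal date would create the opposite error, because events that prompted removal would be relabelled as caused by it.

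The cost is a few protocol sentences, at most one eCRF option, a small number of queries and one extra table. No visit, assessment or clinical rule changes.

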15.4 Serious Adverse Event and Adverse Event Severity

The Investigator will assess the severity of the AE using the following general quidelines:

- **Mild:** An AE that is usually transient, requiring no special treatment, and does not interfere with the subject's daily activities.
- **Moderate**: An AE that introduces a low level of inconvenience or concern to the subject and may interfere with daily activities, but is usually ameliorated by simple therapeutic measures.
- **Severe**: An AE that interrupts a subject's usually daily activity and typically requires systemic drug therapy or other treatment (a severe AE may not necessarily qualify as an SAE).
- **Life-threatening**: An AE that put the subject at immediate risk of death from the event as it occurred. This does not include an event that might have led to death if it had occurred with greater severity.

15.5 Adverse Event Outcome

The Investigator will categorize the outcome of each SAE and AE according to the definitions below:

- Resolved: The subject recovered from the SAE or AE.
- **Resolved with sequelae**: a condition whereby the consequences of a disease or injury include lingering effects.
- Ongoing: At the time of the last assessment, the event is ongoing, with an undetermined outcome. Note: Ongoing SAEs and AEs are not considered resolved as a result of death and no SAE or AE stop date should be recorded for an AE that is ongoing at the time of death.
- Fatal: Adverse Event directly caused death. The Sponsor may request that the Investigator perform or arrange for the conduct of supplemental measurements and/or evaluations. If a subject dies during participation in the study or during a recognized follow-up period, the Sponsor should be provided with a copy of any post-mortem findings, including histopathology. Note: Death is an *outcome* of an adverse event and not an adverse event in itself. All reports of subject death should include an adverse event term (other than "Death") for the cause of the death.

Since reporting of an SAE is required within 24 hours of discovery, Death can be reported as an initial event term and updated to the final diagnosis in a follow-up report. If an adverse event term is not provided, the Investigator will be queried to obtain the cause of death. Only in the rare occurrence that no verbatim description of an adverse event can be obtained from the investigative site will "Death – Unknown Cause" be used as the event term.

The Investigator should attempt to establish a diagnosis of the event based on the signs, symptoms and/or other clinical information. In such cases, the diagnosis should be documented as the AE (and SAE if serious) and not the individual signs/symptoms.

In the case of abnormal labs or diagnostic tests judged to be clinically significant by the Investigator a diagnosis, if known, or clinical signs or symptoms if the diagnosis is unknown, rather than the clinically significant laboratory finding or abnormal assessment, should be used to complete the AE or SAE eCRF. If no diagnosis is known and clinical signs or symptoms are not present, then the abnormal finding should be recorded on the AE or SAE eCRF. If an SAE report is completed, pertinent laboratory data should be recorded on the SAE eCRF, preferably with baseline values and copies of laboratory reports.

15.6 Prompt Reporting of SAEs to Sponsor

The Sponsor has requirements for reporting serious adverse events to regulatory agencies for a drug under clinical investigation. The Sponsor must be notified **within 24 hours of discovery** and the Investigator determines that an adverse event meets the protocol definition of an SAE.

All SAEs occurring from the beginning of study entry through study exit require immediate reporting to the Sponsor. Investigators should not wait to receive additional information to fully document the event prior to notifying the Sponsor

but should provide as much relevant information as immediately available. Further details of the event can be provided as they become available. The procedures for reporting SAEs are as follows:

- Complete the "Serious Adverse Event Report" form;
- Submit the completed form to Sponsor;
- For fatal or life-threatening events, also submit copies of hospital case reports, autopsy reports, and other documents when requested and applicable;
- The Sponsor may request additional information from the Investigator to ensure the timely completion of accurate safety reports;
- Any fatal or life-threatening events should also be reported immediately by telephone to Sponsor;
- The SAE eCRF should be completed as thoroughly as possible and signed by the Investigator before transmittal to Sponsor. It is very important that the Investigator provides an assessment of the causal relationship between the event and the study device at the time of the initial report; and
- The Investigator, or responsible person according to local requirements, must comply with the applicable local regulatory requirements concerning the reporting of SAEs to regulatory authorities and the IRB.

15.7 Clinical Laboratory Abnormalities and Other Abnormal Assessments as Adverse Events and Serious Adverse Events

Abnormal laboratory findings (e.g., clinical chemistry, hematology) or other abnormal assessments (e.g., electrocardiogram, X-rays, vital signs) per se are not reported as AEs. However, abnormal findings that are deemed **clinically significant** (i.e., associated with signs and/or symptoms or requiring therapeutic intervention) must be recorded as AEs if they meet the definition of an adverse event (and recorded as an SAE if they meet the criteria of being serious) as described previously. Clinically significant abnormal laboratory or other abnormal findings that are detected after study device placement or that are present at baseline and worsen following the placement of VeraCept are included as AEs (or SAEs if serious).

The Investigator should exercise his or her medical judgment in deciding whether an abnormal laboratory finding or other abnormal assessment is clinically significant. A clinically significant laboratory abnormality in the absence of clinical symptoms may also jeopardize the subject and may require intervention to prevent immediate consequences (e.g., a markedly high serum potassium concentration may not be accompanied by arrhythmia, yet be of a magnitude to require potassium-binding resin administration to prevent such

sequelae). Subjects should undergo repeat testing of clinically significant abnormal laboratory findings as soon as they are recognized.

15.8 Documenting Adverse Events

Any AE occurring from the beginning of the study device placement procedure through Study Exit must be documented in the subject's study records and on the AE eCRF. SAEs that occur during the study must be documented in the subject's study record, on the AE eCRF and on the SAE eCRF as appropriate.

The investigator's assessment of causality, severity and status of the adverse event must be documented. When a causality assessment is provided for a serious adverse event, it is important to include a rationale for the assessment so that a better understanding of the reported event can be compiled. The rationale should be accompanied by all available supporting evidence, including relevant laboratory tests, histopathology evaluations and the results of other diagnostic procedures. The Investigator's rationale with supporting evidence is valuable when Sponsor performs a cumulative analysis of similar events.

15.9 Follow-up of Adverse Events and Serious Adverse Events

All AEs and SAEs must be followed until resolution, the condition stabilizes, 30 days post study device removal, or the subject dies or is lost to follow-up (including withdrawal of consent), whichever occurs first. The Investigator is responsible to ensure that follow-up includes any supplemental investigations as may be indicated to elucidate as completely as practical the nature and/or causality of the AE/SAE. This may include additional laboratory tests or investigations, histopathologic examinations, or consultation with other health care professionals. Follow-up information should be submitted to the Sponsor in a timely many as the information is obtained.

15.10 Clarification in Reporting of Deaths

All subject deaths (regardless of relationship to study device) should be reported that occur from the beginning of study device placement through Study Exit. The information should be recorded on the Subject Death form and the SAE eCRF.

15.11 Post-Study Treatment Reporting Requirements

For all enrolled subjects, all AEs and SAEs, regardless of cause or relationship, that occur from the beginning of study device placement through Study Exit require reporting to the Sponsor. In addition, if the Investigator learns of any SAE at any time after a subject has had the study device removed, and such event seems reasonably related to study drug, the Investigator should immediately notify the Sponsor.

15.12 Study Device Malfunction

Should the study device not perform mechanically as expected, it is essential that it be returned to the study Sponsor for assessment.

16. PROTOCOL VIOLATIONS and DEVIATIONS

Except in the event of a medical emergency or where it is necessary to protect the safety, rights or welfare of the study subject, any changes to the protocol will require written approval of ContraMed LLC or designee. Violations or deviations from the Clinical Investigational Plan to protect the health and safety of the subject will be reported to the IRB and as required by local regulations. All protocol violations or deviations will be recorded on the case report forms (eCRFs). A protocol violation or deviation may be requested in advance of implementation and will be reviewed for approval by ContraMed or its designee, or a violations/deviation may be identified after the fact, by the Investigator, ContraMed, or the monitoring staff. Investigators will be asked to provide an explanation for the all violations and deviations identified. ContraMed, or designee, will be responsible for analyzing deviations and may implement corrective actions as necessary.

